10.1 Populations for analysis

The safety set (SS) will consist of all enrolled patients for whom safety information was collected. Of note, the statement that a patient had no adverse events also constitutes a safety assessment.

The Full Analysis Set (FAS) will consist of all enrolled patients for whom data was collected and who have at least one post-baseline efficacy assessment. This will be analogous to the ITT population.

The Per Protocol Population will consist of all patients from the FAS-population, for whom no major protocol violations are reported. All reported protocol violations will be classified as minor or major in a data review meeting prior to data base lock.

10.2 Patient demographics/other baseline characteristics

Background and demographic characteristics will be presented using summary statistics.

Summary statistics will include n (number of observations), mean, standard deviation, median, minimum and maximum values for continuous variables, as well as frequencies and percentages for categorical variables.

10.3 Treatments (study drug, rescue medication, other concomitant therapies, compliance)

All patients will receive a dose of 0.5 mg fingolimod daily according to local label. No study drug will be provided.

Concomitant therapy used both prior to and after start of study drug administration will be summarized by treatment group. The WHO Drug Reference Guide will be used for coding of medications.

10.4 Analysis of the primary objective(s)

10.4.1 Variable

The primary outcome of interest is the rate and pattern of change in RNFL thickness in RRMS patients treated with fingolimod from baseline to month 36 as assessed by OCT.

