3.1 Primary objective

To evaluate the change in average RNFL thickness (RNFLT) in RRMS patients treated with fingolimod over 36 months as assessed by OCT

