10.4.2 Statistical hypothesis, model, and method of analysis

The primary efficacy variable will be presented graphically to investigate the pattern of change over time. Change will be assessed from baseline to month 12, month 12 to month 24, month 24 to month 36. Change will be presented as absolute changes, as well as percent change. Pairwise comparisons will be performed using a t-test. No adjustment for multiple comparisons will be made. Additionally, change from baseline to month 12, 24, and 36 will be analyzed using a paired t-test under the assumption of normal distribution for the ITT population. In case of non-normality a Wilcoxon signed-rank test will be applied instead.

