2.5 Analysis of the primary objective

2.5.1 Primary endpoint

The primary endpoint is the change, i.e. difference, in mean RNFLT from baseline to month 36 (or last values in case of missing data) in the full analysis set. Mean RNFLT is the average of valid measurements of the right and left eye.

Sensitivity analyses are performed with the Per-Protocol Set (PPS) and for the relative change assessed by the M36/BL.

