2.5.2 Statistical hypothesis, model, and method of analysis

No hypothesis is to be tested.

Descriptive pairwise comparisons are performed using a paired t-test in case of normality, In case of non-normality a Wilcoxon signed-rank test is applied instead. No adjustment for multiple comparisons are made. For each parameter the normality distribution is graphically proved for the change from BL to M36. Differences as well as pre-post ratios are displayed. When non-normality is detected for the change to M36 the changes to M12 respectively M36 are analysed also non-parametrically.

The primary efficacy variable is presented graphically by standard boxplots for each time point. Sample statistics are presented for each time point and changes (differences as well as ratios) to each time point.

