2.14 Interim analysis

Not applicable.

3 Sample size calculation

Published data varies widely as to the average thinning of RNFL in MS patients and no data is available on patients treated with Fingolimod. As this is an explorative study to get a better understanding of RNFL thinning in RRMS treated with Fingolimod we will take a representative sample of approximately 100 patients with RRMS who are stable on Fingolimod

4 Change to protocol specified analyses

[figure not shown]
The change in ganglion cell layer thickness (GCLT) was defined as secondary endpoint, but OCT measured the ganglion cell inner plexiform layer (GCIP). This was done because both layers are not clearly separable by OCT. The volume of GCIP is declared as usual parameter.

5 Appendix

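### The SAP leaves out the protocol's month 12–24 and month 24–36 RNFLT changes and any rate of change, and does not declare the omission

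*Protocol*

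**What the plan says.** **Protocol.** The primary objective (3.1) is worded as a change over the whole period: "To evaluate the change in average RNFL thickness (RNFLT) in RRMS patients treated with fingolimod over 36 months as assessed by OCT". Section 10.4.1 turns this into a variable: "The primary outcome of interest is the rate and pattern of change in RNFL thickness". Section 10.4.2 sets the intervals: "Change will be assessed from baseline to month 12, month 12 to month 24, month 24 to month 36". These are to be shown in absolute and percent terms, with pairwise t-tests and no multiplicity adjustment. A second set of analyses follows: "Additionally, change from baseline to month 12, 24, and 36 will be analyzed using a paired t-test".

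**SAP.** Section 2.5.1 reads: "The primary endpoint is the change, i.e. difference, in mean RNFLT from baseline to month 36", with the last value used where month 36 is missing. Section 1.2 adds differences and ratios from baseline to months 12 and 24 as secondary endpoints, under the same replacement rule. Section 2.5.2 plans boxplots at each time point, and "Sample statistics are presented for each time point and changes (differences as well as ratios) to each time point". Section 2.5.3 carries post-baseline values forward and adds a sensitivity analysis without replacement. Section 4, which records departures from the protocol's analyses, has one entry: "The change in ganglion cell layer thickness (GCLT) was defined as secondary endpoint", followed by the reason why a combined layer was measured instead.

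**The concern.** The intervals come first in the protocol's primary analysis, and the changes from baseline are the addition. The SAP keeps the addition and omits the intervals, and no rate appears. The protocol's variable asks about the course of thinning over three years on fingolimod. That needs an estimate for each year, with its uncertainty, from the same patients at both ends of the year. Without a planned estimate, a reader of the report would subtract one cumulative mean from the next. The result has no standard error and, with last values carried forward, leans towards apparent slowing. Because the omission is undeclared, nobody reading the SAP can tell whether it was deliberate.

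**Working it through.** The planned size of about 100 has no effect size, SD or power behind it, so the plan gives no figure to reproduce. The check is a comparison of texts, followed by a test of whether the planned outputs could replace the omitted ones.

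**1. Side by side**

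| Item in Protocol 10.4.1–10.4.2 | Counterpart in the visible SAP |
|---|---|
| Baseline to month 12 | Yes (1.2, secondary) |
| Month 12 to 24 | None named |
| Month 24 to 36 | None named |
| Baseline to months 24 and 36 | Yes (1.2, 2.5.1) |
| Rate | None: no slope, yearly rate or longitudinal model |
| Pattern | In part: boxplots and per-visit statistics (2.5.2) |

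The only mixed model (2.5.4, 5.3.2) compares eyes with and without optic neuritis on the change from baseline to the last value until month 36.

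**2. Point estimates by subtraction.** In one fixed set of patients, mean(M24 − M12) = mean(M24 − BL) − mean(M12 − BL). This is an identity, so in the full analysis set with last values carried forward the interval means can be recovered exactly.

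**3. Precision cannot be recovered.** Let A and B be the changes from baseline to months 24 and 12. Then Var(A − B) = Var A + Var B − 2 Cov(A, B). If both have the same SD (an assumption) and correlation ρ, the 95% half-width at n = 100 is 1.96 × √(2 − 2ρ) / √100, in units of that SD:

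| ρ | Half-width |
|---|---|
| 0.3 | 0.232 |
| 0.5 | 0.196 |
| 0.7 | 0.152 |
| 0.9 | 0.088 |

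A single change from baseline has 1.96 / √100 = 0.196. The interval's precision therefore depends on ρ. SAP 2.7.2 plans correlations of changes from baseline, but the visible text does not say that they are of RNFLT across visits.

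**4. Effect of carry-forward on the subtracted means.** Assume a true loss of 1 unit per year in everyone, nobody missing at month 12, and dropout that is permanent once it occurs. The documents give no dropout figure. With 10% missing at month 24 and 20% at month 36:

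- Month 12: 1.00
- Month 24: 0.90 × 2 + 0.10 × 1 = 1.90
- Month 36: 0.80 × 3 + 0.10 × 2 + 0.10 × 1 = 2.70
- Yearly losses by subtraction: 1.00, 0.90, 0.80

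Over a range of assumed missingness:

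| Missing at M24 / M36 | Apparent yearly losses |
|---|---|
| 5% / 10% | 1.00, 0.95, 0.90 |
| 10% / 20% | 1.00, 0.90, 0.80 |
| 15% / 30% | 1.00, 0.85, 0.70 |

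The true value is 1.00 in every year.

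**5. The sensitivity analysis without replacement.** Here the patients contributing at months 12, 24 and 36 can differ. The identity in step 2 then fails, and subtraction mixes within-patient change with a change in who is measured.

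**The case against.** The strongest defence has four parts.

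- **The SAP follows the protocol's objective.** Protocol 3.1 and section 11 speak of change over 36 months, and the protocol gives no formula for a rate. This stands as far as it goes, and the month 36 difference is a legitimate primary summary. It does not explain the loss of intervals that 10.4.2 spells out.
- **The course can be seen anyway.** A reader might infer from the omission that the study could not show whether thinning slows or continues, or that only one 36-month figure would be reported. The documents do not support that. Changes to months 12, 24 and 36 are all planned, with boxplots and per-visit statistics, and courses that differ by year would show up in them.
- **The study is exploratory.** No hypothesis is tested, and the intervals can be derived later from scans already scheduled. That limits the severity. It also means that description with honest uncertainty is the study's main product.
- **The absence is not certain.** Parts of the SAP were removed before review. The pairwise comparisons and the changes to each time point in 2.5.2 name no reference visit. Sections 1.2 and 2.5.1 define change from baseline, so that is the likelier reading, but not the only possible one. If intervals were meant, the SAP needs to say so.

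**Conclusion.** The point holds as an undeclared gap between protocol and SAP in the primary analysis. It should be corrected, but it does not invalidate the study. No visible planned output gives the within-patient month 12–24 or month 24–36 change with an SD, interval or test, and none gives a rate. The makeshift route through carried-forward means is biased towards slowing when thinning is steady. Under the missingness assumed above, the third-year loss is understated by 10% to 30%. Those figures rest on constant loss, the same in patients who drop out and those who stay. They illustrate the direction and order of size and do not predict this trial. Confidence is moderate, for the reasons given about the SAP text.

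**What to change.** - **Intervals.** In SAP 1.2 and 2.5.2, add the paired month 12–24 and month 24–36 RNFLT changes beside baseline to month 12, absolute and percent. Use observed values without carry-forward. Report n, mean, SD, 95% CI and the protocol's paired comparison as a descriptive measure, stating which changes are compared.
- **Rate.** Report a slope per year with 95% CI from a mixed model on all observed visits, with time taken from actual scan dates. This is preferable to a two-point annualised change per patient, which cannot show pattern. It is also noisy when the last scan is early: for a last scan at month 3, dividing by 0.25 years multiplies measurement error by four. A single slope assumes steady change, so it belongs beside the interval changes and does not replace them.
- **Declaration.** If any part is dropped on purpose, list and justify it in SAP section 4.

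The cost is SAP wording, one model and a few table rows, with no extra scans. The interval analyses use only patients scanned at both ends, so n will be smaller by an amount that the documents do not let us state. Showing n for each interval makes that visible.

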10.4.2 Statistical hypothesis, model, and method of analysis

The primary efficacy variable will be presented graphically to investigate the pattern of change over time. Change will be assessed from baseline to month 12, month 12 to month 24, month 24 to month 36. Change will be presented as absolute changes, as well as percent change. Pairwise comparisons will be performed using a t-test. No adjustment for multiple comparisons will be made. Additionally, change from baseline to month 12, 24, and 36 will be analyzed using a paired t-test under the assumption of normal distribution for the ITT population. In case of non-normality a Wilcoxon signed-rank test will be applied instead.

10.4.3 Handling of missing values/censoring/discontinuations

Due to the definition of the FAS-population, all patients in this population will have at least one post-baseline OCT assessment and hence, no imputation of data is necessary.

10.4.4 Supportive analyses

Additionally, the per-protocol population will be analyzed for the primary endpoint.

10.5 Analysis of secondary [REDACTED] objectives

10.5.1 Secondary [REDACTED] outcomes

Secondary endpoints like changes in quadrant RNFLT, changes in total macular volume (TMV), and changes in ganglion cell layer thickness (GCLT) from baseline to months 12, 24, and 36 will be evaluated with a paired t-test or Wilcoxon signed-rank test, as appropriate.

Changes in OCT parameters between eyes with and without history of optic neuritis will be evaluated with a paired t-test or Wilcoxon signed-rank test, as appropriate.

[REDACTED]

Additionally, means, standard deviations, median, minimum and maximum will be presented for each visit, as will be the change from baseline. These descriptive statistics will also be presented for the primary endpoint.

For all other [REDACTED] endpoints summary statistics will be presented. Summary statistics will include n (number of observations), mean, standard deviation, median, minimum and maximum values at each visit, as well as the change.

10.5.2 Tolerability

Not applicable.

10.5.3 Resource utilization

Not applicable.

[REDACTED]

10.5.5 Pharmacokinetics

Not applicable.

10.5.6 Pharmacogenetics/pharmacogenomics

Not applicable.

10.5.7 Biomarkers

10.5.8 Not applicable.PK/PD

Not applicable.

10.6 Interim analysis

No interim analysis is planned

10.7 Sample size calculation

Published data varies widely as to the average thinning of RNFL in MS patients and no data is available on patients treated with Fingolimod. As this is an explorative study to get a better understanding of RNFL thinning in RRMS treated with Fingolimod we will take a representative sample of approximately 100 patients with RRMS who are stable on Fingolimod.

10.8 Power for analysis of critical secondary variables

[figure not shown]
Not applicable.

11 Discussion and rationale for study design features

This study will describe the long-term changes of OCT parameters in RRMS patients treated with oral fingolimod.

This is a prospective, 3-year, open-label study in MS patients treated with fingolimod. It is designed to evaluate the change in average RNFL thickness in this patient population based on a disease modifying treatment with fingolimod. Approximately 100 patients will be enrolled to receive representative data from various centers. In the forefront of the study MS patients are screened for meeting eligibility criteria based on the defined criteria.

In detail, the primary objective of the study is to evaluate the change in average RNFL thickness (RNFLT) in RRMS patients treated with fingolimod from baseline to month 36 as assessed by OCT.

Design, study drug and control

As this trial aims to investigate changes in OCT parameters of RRMS patients treated with the disease modifying substance fingolimod, an open-label design was chosen. All patients will receive a dose of 0.5 mg fingolimod daily according to local label. No study drug will be provided.

Choice of control

Not applicable.

Choice of design

This is a prospective, multi-center, open-label study. An observation time of 3 years is needed to gain a better understanding of the long term changes of optical coherence tomography (OCT) parameters in RRMS patients under treatment with fingolimod. The study is designed to longitudinally investigate the degeneration of retinal axons by measuring change in RNFL thickness by latest OCT-technology. Correlations of OCT findings with available MRI data and clinical findings may enhance our understanding of the relationship between CNS inflammation, tissue injury, regeneration and neurological deficit in context of fingolimod therapy

Data analysis

A total of about 100 patients will be enrolled. Details on data analysis and the definition of the analysis sets are presented and discussed in section 10.

12 References (available upon request)

- Alonso A, Hernán MA (2008). Temporal trends in the incidence of multiple sclerosis: a systematic review. *Neurology* 8;71(2):129-35.

Appendix 1: Administrative procedures

Regulatory and ethical compliance

This clinical study was designed and shall be implemented and reported in accordance with the ICH Harmonized Tripartite Guidelines for Good Clinical Practice, with applicable local regulations (including European Directive 2001/20/EC, US Code of Federal Regulations Title 21, and Japanese Ministry of Health, Labor, and Welfare), and with the ethical principles laid down in the Declaration of Helsinki.

Responsibilities of the investigator and IRB/IEC/REB

The protocol and the proposed informed consent form must be reviewed and approved by a properly constituted Institutional Review Board/Independent Ethics Committee/Research Ethics Board (IRB/IEC/REB) before study start. Approval letters concerning protocol and informed consent will be filed by Novartis. Prior to study start, the investigator is required to sign a protocol signature page confirming his/her agreement to conduct the study in accordance with these documents and all of the instructions and procedures found in this protocol and to give access to all relevant data and records to Novartis monitors, auditors, Novartis Clinical Quality Assurance representatives, designated agents of Novartis, IRBs/IECs/REBs, and regulatory authorities as required. If an inspection of the clinical site is requested by a regulatory authority, the investigator must inform Novartis immediately that this request has been made.

Informed consent

Eligible patients may only be included in the study after providing written, IRB/IEC/REB-approved informed consent.

Informed consent must be obtained before conducting any study-specific procedures (i.e., all of the procedures described in the protocol). The process of obtaining informed consent should be documented in the patient source documents.

Novartis will provide to investigators in a separate document a proposed informed consent form that complies with the ICH GCP guideline and regulatory requirements and is considered appropriate for this study.

Amendments to the protocol

Any change or addition to the protocol can only be made in a written protocol amendment that must be approved by Novartis, the Health Authority and the IRB/IEC/REB. Only amendments that are required for patient safety may be implemented prior to IRB/IEC/REB approval. Notwithstanding the need for approval of formal protocol amendments, the investigator is expected to take any immediate action required for the safety of any patient included in this study, even if this action represents a deviation from the protocol. In such cases, Novartis should be notified of this action and the IRB/IEC/REB at the study site should be informed within 10 working days.

Discontinuation of the study

Novartis reserves the right to discontinue this study under the conditions specified in the clinical trial agreement.

Appendix 2: Blood Collection Log

This is only an overview on the total volume of blood collected for local laboratory assessments at the study visits.

	Routine Laboratory = Total blood volume		
V1 (Screening)	10 ml		
V3	10 ml		
V4	10 ml		
V5	10 ml		
V6	10 ml		
V7	10 ml		

Appendix 3: Clinically notable vital signs

Only selected laboratory parameters which have been shown to be sensitive to fingolimod exposure are included.

CRITERIA FOR NOTABLE LABORATORY ABNORMALITIES

Notable Values		
Laboratory Variable	Standard Units	SI Units
LIVER FUNCTION AND RELATED VARIABLES		
SGOT (AST)	>3x ULN, <5x ULN F: > 105 U/L <175 U/L, M: >150 U/L <250 U/L>	F: > 105 U/L <175 U/L M: >150 U/L <250 U/L
Gamma Glutamyltransferase	> 130 U/L	> 130 U/L
SGPT (ALT)	>3x ULN, <5x ULN F: > 105 U/L <175 U/L, M: >150 U/L <250 U/L	F: > 105 U/L <175 U/L M: >150 U/L <250 U/L
Alkaline Phosphatase	> 280 U/L	> 280 U/L
Total bilirubin	≥ 2.0 mg/dL	≥ 34.2 μmol/L
RENAL FUNCTION / METABOLIC AND ELECTROLYTE VARIABLES		
Glucose	≥200 mg/dL	≥11.1 mmol/L
Creatinine	≥2.0 mg/dL	≥176 umol/L
Chloride	≤ 85 mEq/L ≥ 119 mEq/L	≤ 85 mmol/L ≥ 119 mmol/L
BUN	≤ 2 mg/dL ≥ 30 mg/dL	≤ 0.7 mmol/L ≥ 10.7 mmol/L
Sodium	< 130 mEq/L > 150 mEq/L	< 130 mmol/L >150 mmol/L
Potassium	≤ 3.0 mEq/L ≥ 6.0 mEq/L	≤ 3.0 mmol/L ≥ 6.0 mmol/L
Calcium	≤ 7.5 mg/dL ≥ 11.6 mg/dL	≤ 1.87 mmol/L ≥ 2.89 mmol/L
HEMATOLOGY VARIABLES		
Hemoglobin	≤10.0 g/dL	≤100 g/L
Platelets (Thrombocytes)	≤100 k/mm ³ ≥600 k/mm ³	≤100 x 10 ⁹ /L ≥600 x 10 ⁹ /L
Leukocytes (WBCs)	≤2.0 k/mm ³ ≥15 k/mm ³	≤2.0 x 10 ⁹ /L ≥15 x 10 ⁹ /L
Red blood cells RBCs	<3,300,000/mm ³ >6,800,000/mm ³	<3.3 x 10 ¹² /L >6.8 x 10 ¹² /L
HEMATOLOGY VARIABLES: DIFFERENTIAL		

Notable Values		
Lymphocytes	<100/mm ³ ≥8000/mm ³	<0.1 x 10 ⁹ /L ≥8 x 10 ⁹ /L

NOTABLE VITAL SIGNS	
Vital Sign Variable	Notable Criteria
Pulse (beats/min)	>120bpm or Increase of ≥ 15 bpm from baseline Or < 50bpm or Decrease of ≥ 15 bpm from baseline
Systolic BP (mmHg)	≥ 140 mmHg or Increase of ≥ 20 mmHg from baseline Or ≤ 90 mmHg or Decrease of ≥ 20 mmHg from baseline
Diastolic BP (mmHg)	≥ 90 mmHg or Increase of ≥ 15 mmHg from baseline Or ≤ 50 mmHg or Decrease of ≥ 15 mmHg from baseline

Appendix 4: 2010 Revisions to the McDonald diagnosis criteria for MS

Guidelines from International Panel on the diagnosis of MS

(Polman et. al, 2011)

Clinical Presentation	Additional Data Needed for MS Diagnosis
2 or more attacks ^a ; objective clinical evidence of 2 or more lesions or objective clinical evidence of 1 lesion with reasonable historical evidence of a prior attack ^b	None ^c
2 or more attacks ^a ; objective clinical evidence of 1 lesion	Dissemination in space, demonstrated by 
 • ≥ 1 T2 lesion in at least two out of four MS-typical regions of the CNS (periventricular, juxtacortical, infratentorial, or spinal cord)^d OR 
 • Await a further clinical attack^a implicating a different CNS site
1 attack ^a ; objective clinical evidence of 2 or more lesions	Dissemination in time, demonstrated by 
 • Simultaneous presence of asymptomatic gadolinium-enhancing and non-enhancing lesions at any time. OR 
 • A new T2 and/or gadolinium-enhancing lesion(s) on follow-up MRI, irrespective of its timing with reference to a baseline scan. OR 
 • Await a second clinical attack^a
1 attack ^a ; objective clinical evidence of 1 lesion (clinically isolated syndrome)	Dissemination in space and time, demonstrated by: 
For DIS
 
 • ≥ 1 T2 lesion in at least two out of four MS-typical regions of the CNS (periventricular, juxtacortical, infratentorial, or spinal cord)^d OR 
 • Await a second clinical attack^a implicating a different CNS site 
AND
 
For DIT
 
 • Simultaneous presence of asymptomatic gadolinium-enhancing and non-enhancing lesions at any time. OR

	
 • A new T2 and/or gadolinium-enhancing lesion(s) on follow-up MRI, irrespective of its timing with reference to a baseline scan. 
OR
 
 • Await a second clinical attack^a

Insidious neurological progression suggestive of MS (PPMS)
	
One year of disease progression (retrospectively or prospectively determined) PLUS Two out of the three following criteria^d
 
 1. Evidence for DIS in the brain based on ≥ 1 T2+ lesions in the MS-characteristic periventricular, juxtacortical or infratentorial regions 2. Evidence for DIS in the spinal cord based on ≥ 2 T2+ lesions in the cord 3. Positive CSF (isoelectric focusing evidence of oligoclonal bands and/or elevated IgG index)

If the Criteria are fulfilled and there is no better explanation for the clinical presentation, the diagnosis is MS; if suspicious, but the Criteria are not completely met, the diagnosis is “possible MS”; if another diagnosis arises during the evaluation that better explains the clinical presentation, then the diagnosis is “not MS.”

a. An attack (relapse; exacerbation) is defined this as patient-reported or objectively observed events typical of an acute inflammatory demyelinating event in the CNS, current or historical, with duration of at least 24 hours, in the absence of fever or infection. It should be documented by contemporaneous neurological examination, but some historical events with symptoms and evolution characteristic for MS, but for which no objective neurological findings are documented, can provide reasonable evidence of a prior demyelinating event. Reports of paroxysmal symptoms (historical or current) should, however, consist of multiple episodes occurring over not less than 24 hours. Before a definite diagnosis of MS can be made, at least one attack must be corroborated by findings on neurological examination, visual evoked potential (VEP) response in patients reporting prior visual disturbance, or MRI consistent with demyelination in the area of the CNS implicated in the historical report of neurological symptoms.

b. Clinical diagnosis based on objective clinical findings for two attacks is most secure. Reasonable historical evidence for one past attack, in the absence of documented objective neurological findings, can include historical events with symptoms and evolution characteristics for a prior inflammatory demyelinating event; at least one attack, however, must be supported by objective findings.

c. No additional tests are required. However, it is desirable that any diagnosis of MS be made with access to imaging based on these Criteria. If imaging or other tests

^aGadolinium-enhancing lesions are not required; symptomatic lesions are excluded from consideration in subjects with brainstem or spinal cord syndromes.

MS = multiple sclerosis; CNS = central nervous system; MRI = magnetic resonance imaging; DIS = dissemination in space; DIT = dissemination in time; PPMS = primary progressive multiple sclerosis; CSF = cerebrospinal fluid; IgG = immunoglobulin G

